The CO₂RE system device is FDA-cleared under a 510(k) K151655 - intended for laser incision, excision, ablation, and/or vaporization of soft tissue in gynecology (GYN) for the treatment of: conization of the cervix, including cervical intra-epithelial neoplasia (CIN) and vulvar and vaginal intra-epithelial neoplasia (VIN, VAIN); condyloma acuminata, including cervical, genital, vulvar, perineal, and Bowen's disease (Erythroplasia of Queyrat) and Bowenoid papulosa (BP) lesions; and leukoplakia (vulvar dystrophies).

STUDY DESIGN

Study Duration and Timelines

This study is a prospective, non-randomized, single group assignment, interventional clinical trial to evaluate the CO₂RE laser device for safety and efficacy for vulvar lichen sclerosus (vulvar dystrophy) treatment.

Up to a total of 45 female candidates, seeking treatment for vulvar lichen sclerosus from the participating investigator will be enrolled at a participating study site. Subjects will receive up to five (5) CO₂RE treatments.

A 1-week post first treatment safety call will be performed by a study nurse to review the patient daily diary.

Each subject will be followed for 4 additional post treatment visits (FU visits) that will be conducted at:

- 6 weeks post last treatment – 6wk FU ± 2 weeks (Efficacy & Safety).
- 3 months post last treatment – 3m FU ± 2 weeks (Efficacy & Safety).
- 6 months post last treatment – 6m FU ± 2 weeks (Efficacy & Safety).

- 12 months post last treatment – 12m FU ± 2 weeks (Efficacy & Safety).

STUDY OBJECTIVES AND END POINTS

Primary Objective

To evaluate the efficacy of a series of CO₂RE treatments to improve the symptoms, clinical signs, and architectural changes associated with vulvar lichen sclerosus, at 6 weeks, 3 months, 6 months and 12 months after the final treatment.

Secondary Objectives

1. Evaluate sexual function at the 3-month and 6-month follow-ups compared to baseline.
2. Evaluate histological markers at the 6-week and 6-month follow-up compared to baseline.
3. Evaluate discomfort following each treatment.
4. Evaluate the safety of CO₂RE treatments for VLS during the study.
5. Evaluate subject satisfaction at the 6-week, 3-month, 6-month and 12-month follow-up visits.

Primary Endpoint

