Change from baseline in presence and severity of symptoms (5-point severity scale), clinical signs (3-point severity scale) and architectural changes (3-point severity scale) at the 6-week, 3-month, 6-month and 12-month follow-up visits. (**Appendices I & II**).

Secondary Safety Endpoints

Evaluate the safety of the treatment:

1. Clinical evaluation of treated area at each study visit. Clinical photography will be performed for study documentation (**Appendix IV**).
2. Pain/discomfort level using a 10-point Numerical Scale Response (NSR) after each treatment (**Appendix V**).
3. Number, severity and type of adverse events recorded throughout course of the study.
4. 1 week ± 2 days post first treatment safety phone call (review of 1-week patient diary) – (**Appendix VI**).

Secondary Efficacy Endpoints

1. Sexual function, using the Female Sexual Function Index (**Appendix III**), at baseline and at the 3-month and 6-month follow-ups. *An overall score ≤ 26.55 is classified as Female Sexual Disorder (FSD).*¹⁵
2. Histological signs (degree of hyperkeratosis, epidermal atrophy and dermal inflammation) at baseline and at 6 weeks and 6 months after the final treatment.
3. Subject satisfaction, using a 5-point Likert scale (-2=very dissatisfied; 2=Very satisfied), will be assessed at the 6-week, 3-month, 6-month and 12-month follow-up visits (**Appendix VII**).

SUBJECT POPULATION

Up to 45 female subjects who meet the following inclusion / exclusion criteria may be enrolled.

Subject Withdrawal and Replacement

Subjects enrolled in the study can discontinue their participation at any time for any reason without prejudice or reduction in the quality of their medical care. The investigator or sponsor can terminate a subject's participation in this study to protect the subject's health or if the subject fails to follow directions resulting in noncompliance to study procedures. Subjects who withdraw or are terminated from the study may be replaced to allow up to 45 subjects to complete the study. Subjects who fail to complete the treatment will be replaced and will not be evaluable.

Inclusion Criteria

1. Able to read, understand and sign informed consent for study participation;
2. Female subjects with age 18-80 years;
3. Biopsy demonstrates biopsy-proven lichen sclerosus and/or there are characteristic changes for vulvar lichen sclerosus on physical examination;

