4. Treatment of LS has been recalcitrant to mid to high-potent topical corticosteroid treatment or subject refuses topical corticosteroid treatment. Recalcitrance to therapy is defined as no response to topical corticosteroids of an adequate potency (i.e. clobetasol propionate 0.05% ointment or other steroids) and a sufficient duration (12 weeks of use) or lack of symptomatic control of the disease with a maintenance therapy;
5. Topical corticosteroid treatment, if any, will be continued during the study period;
6. Exogenous hormone treatment, if any, will be continued during the study period (type and dose must stay consistent throughout the study);

7. One or more of the following symptoms: itch; pain unrelated to intercourse; pain, skin tearing or bleeding with intercourse; changes/decrease in sexual function;
8. Characteristic changes for vulvar lichen sclerosus on physical examination;
9. No breaks, tears or lesions, malodorous discharge or strawberry cervix present on gynecological exam.

Exclusion Criteria

1. Presence of clinically atypical appearing nevi in the area to be treated;
2. Unexplained vaginal bleeding;
3. Active infection, specifically: urinary tract infection, vulvar or vaginal infection (candidiasis, genital herpes/HSV, bacterial vaginosis, trichomonas);
4. History of vulvar or any gynecological malignancy, as well as history of pelvic radiation therapy or stem cell transplant;
5. Pelvic organ prolapse > stage 2;
6. Pregnancy or planning pregnancy during the study;
7. Systemic treatment with immuno-modulatory drugs.
8. Use of vaginal dilators during study.

STUDY PROCEDURES

Enrollment and Screening

During the first visit, the investigator will screen the subject for eligibility to participate in the clinical study. The inclusion/exclusion criteria will be reviewed, the subject's medical history, an examination of the subject's treatment areas will be conducted.

The subject will review the informed consent form (ICF) and the study will be explained to the subject including all risks, potential benefits, procedures, visit requirements, and other alternative treatment options. If the subject qualifies and wishes to participate they will complete the ICF with a signature and date. The original will be retained with subject's records and a copy will be provided to the subject.

The following measurements will be performed and recorded at the specified times throughout the study (as specified in Error! Reference source not found.).

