Table 2. Study Measurements

Assessment	When to conduct	Method
Complete the Inform Consent form and Eligibility Screening and Medical History	During the screening visit / prior to the 1 st treatment	Physician or staff will complete the form with the study subject
PAP smear if not up-to-date (within 3 years according to ACOG guidelines)		Patient should provide lab results of up-to-date normal cell cytology
Urine pregnancy test for women capable of becoming pregnant		Patient should have a negative pregnancy test
Gynecological exam		Physician will examine the vulvar and vaginal area for any signs of active infection or atypical nevi
Vulvar biopsy of treatment area (optional)	Prior to the 1 st treatment and at the 6-week and 6-month follow-ups	Biopsies will be obtained from up to 10 subjects to conduct histological assessment. Lab reports will be provided to show changes in markers compared to baseline.
Subject assessment of symptoms	
 • Baseline or pre-Tx. 1 • At the 6-week, 3-month, 6-month and 12-month follow-up visits 	Subjects will complete the Symptom Severity Questionnaire, according to the pre-defined scales (Appendix I)
Physician assessment	
 • Baseline or pre-Tx. 1 • Prior to treatments • At the 6-week, 3-month, 6-month and 12-month follow-up visits 	Physician will assess clinical signs associated with VLS, according to the pre-defined scales (Appendix II)
Subject assessment of sexual function	
 • Baseline or pre-Tx. 1 • At the 3-month and 6-month follow-up visits 	Subjects will complete the Female Sexual Function Index (FSFI) – Appendix III
Clinical evaluation and photographs of treated area	
 • Baseline or pre-Tx. 1 • Prior to treatments • At the 6-week, 3-month, 6-month and 12-month follow-up visits 	Physician will evaluate the treatment area. Physician or staff will take photographs of the treatment area (Appendix IV)
Treatment pain assessment	Immediately after each treatment	NSR Scale (Appendix V)
Subject 1-week daily diary - reviewed at the 1wk FU after the first treatment	The daily diary will be provided at the 1 st treatment visit and reviewed by phone during the 1-week safety evaluation	Subjects will be requested to complete a daily diary with data regarding their comfort, AE, and activity (7 days of follow-up post 1st treatment) – Appendix VI

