Following the first treatment:

1. Subjects will receive a daily diary, which they will be requested to complete, regarding their comfort and any adverse events for the 7-day period following treatment.

Following each treatment session

1. If the subject experiences itch or discomfort after treatment, ice packs may be applied to the treatment area.
2. Temporary erythema (redness) and edema (swelling), as well as heat and tightening sensations, may occur up to a few hours after the treatment. If the subject feels significant discomfort longer than a few hours, an over-the-counter pain medication such as Tylenol® (Acetaminophen) may be used. Nonsteroidal anti-inflammatory drugs (NSAID), such as aspirin, Ibuprofen (Advil, Motrin), naproxen (Aleve, Anaprox, Naprelan, Naprosyn), etc. should be avoided unless the patient does not experience symptomatic relief with or is contraindicated to acetaminophen.
3. On the evening after the treatment, subjects should wash the treated areas gently with lukewarm water and avoid very hot or cold water in these areas. Generally, subjects may use their regular cleanser after treatment, as long as these are not mechanical scrubs or exfoliants.
4. Subject should refrain from sexual activities for a period of 7 days.
5. Any pain, fever or unusual discharge should be immediately reported.

 Candela Corporation Confidential	Clinical Study of the CO₂RE Laser Device for Treatment of Vulvar Lichen Sclerosus				
	Protocol #	DHF25211	Rev. Date	February 19, 2019	Page 16 of 39

Follow-up Visits

1. All subjects will be requested to return to the clinic at the following time-points during the study to assess the clinical safety and performance of the device:
 - 6 weeks post last treatment – 6wk FU ± 2 weeks.
 - 3 months post last treatment – 3m FU ± 2 weeks.
 - 6 months post last treatment – 6m FU ± 2 weeks.
 - 12 months post last treatment – 12m FU ± 2 weeks.
2. At the follow-up visits, the following assessments will be performed, and data recorded:
 - Review changes in medication, medical history and AE, if applicable, from last visit.
 - Photographs of treated area.
 - Optional biopsy of treated area (6-week and 6-month follow-up only).
 - Subject assessment of symptom severity.
 - Investigator assessment of clinical signs.
 - Subject Satisfaction.

DATA ANALYSIS

Recording

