APPENDIX III – FEMALE SEXUAL FUNCTION INDEX*
Female Sexual Function Index (FSFI) ®

Subject Identifier _____ Date _____

INSTRUCTIONS: These questions ask about your sexual feelings and responses during the past 4 weeks. Please answer the following questions as honestly and clearly as possible. Your responses will be kept completely confidential. In answering these questions the following definitions apply:

Sexual activity can include caressing, foreplay, masturbation and vaginal intercourse.

Sexual intercourse is defined as penile penetration (entry) of the vagina.

Sexual stimulation includes situations like foreplay with a partner, self-stimulation (masturbation), or sexual fantasy.

CHECK ONLY ONE BOX PER QUESTION.

Sexual desire or interest is a feeling that includes wanting to have a sexual experience, feeling receptive to a partner's sexual initiation, and thinking or fantasizing about having sex.

1. Over the past 4 weeks, how often did you feel sexual desire or interest?

- Almost always or always
- Most times (more than half the time)
- Sometimes (about half the time)
- A few times (less than half the time)
- Almost never or never

2. Over the past 4 weeks, how would you rate your level (degree) of sexual desire or interest?

- Very high
- High
- Moderate
- Low
- Very low or none at all

Sexual arousal is a feeling that includes both physical and mental aspects of sexual excitement. It may include feelings of warmth or tingling in the genitals, lubrication (wetness), or muscle contractions.

3. Over the past 4 weeks, how often did you feel sexually aroused ("turned on") during sexual activity or intercourse?

No sexual activity
 Almost always or always
 Most times (more than half the time)
 Sometimes (about half the time)
 A few times (less than half the time)
 Almost never or never

4. Over the past 4 weeks, how would you rate your level of sexual arousal ("turn on") during sexual activity or intercourse?

No sexual activity
 Very high
 High
 Moderate
 Low
 Very low or none at all

5. Over the past 4 weeks, how confident were you about becoming sexually aroused during sexual activity or intercourse?

No sexual activity
 Very high confidence
 High confidence
 Moderate confidence
 Low confidence
 Very low or no confidence

6. Over the past 4 weeks, how often have you been satisfied with your arousal (excitement) during sexual activity or intercourse?

No sexual activity
 Almost always or always
 Most times (more than half the time)

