- About equally satisfied and dissatisfied
- Moderately dissatisfied
- Very dissatisfied

16. Over the past 4 weeks, how satisfied have you been with your overall sexual life?

- Very satisfied
- Moderately satisfied
- About equally satisfied and dissatisfied
- Moderately dissatisfied
- Very dissatisfied

17. Over the past 4 weeks, how often did you experience discomfort or pain during vaginal penetration?

- Did not attempt intercourse
- Almost always or always
- Most times (more than half the time)
- Sometimes (about half the time)
- A few times (less than half the time)
- Almost never or never

18. Over the past 4 weeks, how often did you experience discomfort or pain following vaginal penetration?

- Did not attempt intercourse
- Almost always or always
- Most times (more than half the time)
- Sometimes (about half the time)
- A few times (less than half the time)
- Almost never or never

19. Over the past 4 weeks, how would you rate your level (degree) of discomfort or pain during or following vaginal penetration?

- Did not attempt intercourse
- Very high
- High
- Moderate
- Low
- Very low or none at all

Thank you for completing this questionnaire

Copyright ©2000 All Rights Reserved

Page 5 (of 5)

[figure not shown]

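### The FSFI cut-off of 26.55 is stated for every subject, although 15 of 19 items have a no-activity or no-intercourse answer and eligibility does not require sexual activity

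*Protocol*

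**What the plan says.** Secondary Efficacy Endpoints, item 1, sets the FSFI "at baseline and at the 3-month and 6-month follow-ups" and adds the rule "An overall score ≤ 26.55 is classified as Female Sexual Disorder (FSD". The rule names no subgroup. It cites reference 15, but the protocol's reference list ends at 14, so the source of the cut-off cannot be identified from the protocol.

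The matching secondary objective is "Evaluate sexual function at the 3-month and 6-month follow-ups compared to baseline". Table 2 says "Subjects will complete the Female Sexual Function Index (FSFI) – Appendix III", with no condition on sexual activity.

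On eligibility, the symptom criterion begins "One or more of the following symptoms: itch; pain unrelated to intercourse". Itch alone therefore qualifies. The age range is 18 to 80, and no criterion asks for sexual activity.

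In Appendix III, items 3 to 14 offer the answer "No sexual activity" and items 17 to 19 offer "Did not attempt intercourse". Items 1, 2, 15 and 16 offer neither. The recall window is four weeks. The visible text gives no points per answer and no domain weights.

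Follow-up Visits, item 2, introduces its list with "At the follow-up visits, the following assessments will be performed, and data recorded". The FSFI is not on that list.

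**The concern.** A total score with one threshold can be read the same way in every woman only if every woman can reach either side of it. Here most items can be answered in a way that reports absence of activity, not quality of function. If such answers get low points, the threshold labels an inactive woman as disordered whatever her desire or satisfaction, and a woman who starts or stops sexual activity changes her total without any change in her other answers. The trial has a single arm, so no comparison group shows how activity would change without treatment.

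The follow-up list is a separate and simpler problem. A site working from it could skip the FSFI at 3 or 6 months, and a four-week recall that was not collected cannot be recovered later.

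**Working it through.** The protocol has no calculation to reproduce: the value 26.55 is stated, not derived.

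**Items affected (Appendix III).** Items 3 to 14 give 12 and items 17 to 19 give 3: 12 + 3 = 15 of 19, or 79%. Four items (1, 2, 15, 16) apply to every woman.

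**Assumptions, not in the protocol.** Ordinary answers score 1 to 5. A no-activity or no-intercourse answer scores s, with s = 0 or s = 1. Domain weights are 0.6 (items 1–2), 0.3 (3–6), 0.3 (7–10), 0.4 (11–13), 0.4 (14–16) and 0.4 (17–19).

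**Weight on each group of items.**
- Four universal items: 0.6 × 2 + 0.4 × 2 = 2.0.
- Fifteen affected items: 0.3 × 4 + 0.3 × 4 + 0.4 × 3 + 0.4 × 1 + 0.4 × 3 = 5.2.
- If every answer is worth k, an active woman totals 7.2k (maximum 36) and an inactive woman totals 2.0k + 5.2s.

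**Total of an inactive woman (k from 1 to 5).**
- s = 0: 2.0 to 10.0.
- s = 1: 7.2 to 15.2.

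Both ranges lie wholly below 26.55. As a check on the weights, an unweighted sum with s = 0 is at most 4 × 5 = 20, also below. An unweighted sum with s = 1 could reach 20 + 15 = 35, so the result would not hold there, but a cut-off of 26.55 does not fit a whole-number sum.

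**A woman whose only change is from inactive to active.**

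| Answers worth k | Inactive, s = 0 | Active | Shift, s = 0 (5.2k) | Shift, s = 1 (5.2(k − 1)) |
|---|---|---|---|---|
| 2 | 4.0 | 14.4 | 10.4 | 5.2 |
| 3 | 6.0 | 21.6 | 15.6 | 10.4 |
| 4 | 8.0 | 28.8 (crosses the cut-off) | 20.8 | 15.6 |

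**Effect on the mean of 45 women (s = 0).** The numbers of women are illustrative.
- Net 4 becoming active: 4 × 10.4 / 45 = 0.9 to 4 × 20.8 / 45 = 1.9 points (1.85 before rounding).
- Net 9: 2.1 to 4.2 points.

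**Active, but no intercourse attempted (items 17 to 19 scored 0).** The maximum is 36 − 0.4 × 15 = 30.0, so the cut-off can be exceeded. With all other answers worth 4, the total is 28.8 − 0.4 × 12 = 24.0, below the cut-off.

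**Answers set to missing.** An inactive woman has no total. She is not misclassified, but she drops out of the change from baseline because of her activity status.

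**Follow-up list against Table 2.** Table 2, the secondary objectives and the endpoint all place the FSFI at 3 and 6 months. The Follow-up Visits list has medication, history and adverse-event review, photographs, optional biopsy, symptom severity, clinical signs and satisfaction. It marks biopsy as limited to certain visits, so the FSFI's visit-specific timing does not explain its absence.

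**The case against.** The strongest objection is that scoring and analysis set for a secondary questionnaire normally belong in the SAP, which is not at hand. That stands: the absence of a scoring rule is no finding. What remains is a sentence that the protocol does contain, an unrestricted classification.

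Several stronger readings are tempting, and the documents do not support them:
- A reader might infer that change in activity is definitely counted as change in function. That depends on numeric scoring, which is not printed.
- A reader might infer that treating the answers as missing is an equal failure. For the classification it largely does what is recommended here; its cost is selective loss in the change score.
- A reader might assume that 20% to 50% of women are inactive and conclude that 9 to 22 of 45 have a change score driven by activity. That share is not in the documents, and a woman inactive at both visits has no activity-driven change. Only those who switch do.
- A reader might say the effect dominates the mean change. No expected FSFI change or standard deviation is given to compare it with, and the shifts of 10.4 and 15.6 are under half of 36.

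Two further points stand. The protocol does not name a disorder rate as an endpoint, so how the classification will be reported is open. And resumed activity may itself be a benefit in this disease, so restricting analysis to women active at both visits conditions on something treatment may affect. Appendix III also defines sexual activity more broadly than intercourse, so not attempting intercourse is not the same as inactivity.

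**Conclusion.** The point holds in a conditional form. The protocol applies a fixed cut-off to all women, while 15 of 19 items allow a no-activity or no-intercourse answer and sexual activity is not an entry requirement. Under both weighted numeric scorings tested, an inactive woman cannot exceed 15.2 and is always classed as disordered. With no-activity scored 0, changing activity status alone moves a woman's total by about 10 to 21 points (answers worth 2 to 4), and a net 4 of 45 women moves the mean by about 0.9 to 1.9. With missing scoring, the problem is selective loss of totals. Points, weights and numbers switching are assumptions, so the size in this trial is unknown. The omission of the FSFI from the follow-up list is a plain inconsistency and needs no assumption.

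**What to change.** - Do not apply the 26.55 classification to women who report no sexual activity in the recall window.
- Report the proportion sexually active and, separately, the proportion attempting intercourse, at baseline, 3 months and 6 months.
- Show FSFI change in all women with a total. As a supporting analysis, show it in women active at both compared visits, and say that this conditions on activity after treatment.
- Report items 1, 2, 15 and 16 for all women.
- Add the FSFI at 3 and 6 months to the Follow-up Visits list, in line with Table 2.
- Supply the missing reference 15.

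All of this uses data already planned. The cost is wording, one list entry, a little more analysis and fewer women classified. The inactive share is not given; if it were 20% to 50% (an assumption), 9 to 22 of 45 women would go unclassified at a visit, leaving 23 to 36.
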